2.3 Rationale of the study

Pediatric CRPS is a severe form of chronic pain that often leads to disability and is difficult to treat. Relatively little is known about its underlying physiological mechanisms and psychosocial factors, which might influence success of treatments. This study will extend our knowledge in several ways:

1. Different techniques will be used to identify predictors of long-term recovery. These techniques include questionnaires, sensory tasks, as well as functional magnetic resonance imaging (fMRI), pseudo-continuous arterial spin labeling (pCASL), and diffusion tensor imaging (DTI) scans.
2. In addition to collecting psychosocial data in the children, psychological well-being of the parents and their response to their child's pain will be assessed. Although parental response to their child's pain has been shown as impacting chronic pain, its association with children's CRPS trajectory remains to be defined.
3. Few studies have investigated brain changes in CRPS children before and after treatment. It has not been studied so far whether some of these changes might be predictive of the long-term success of treatment, nor whether these changes differ as a function of the severity of CRPS symptoms.
4. Hypersensitivity to auditory and visual stimuli is sometimes reported anecdotally as an issue in children with CRPS by clinicians. This study will seek to better define if sensory modalities are hypersensitive in patients undergoing treatment for CRPS. In addition, cerebral representations of sensory sensitivity will be analyzed as potential brain markers predicting long-term response to treatment.

2.4 Rationale for the study outcomes

2.4.1 Ratings of pain intensity and unpleasantness

Ratings of pain intensity and unpleasantness will be used to assess reduction in spontaneous and experimental pain following outpatient or inpatient treatments. Visual analog scales (VAS) will be used for this purpose. VAS are commonly used tools to quickly assess different aspects of such sensations. Differences between pain intensity and unpleasantness will be explained to participants, following instructions described in Price et al. (Price, McGrath, Rafii, & Buckingham, 1983).

2.4.2 Pain disabilities

Pain disabilities will be assessed before and after treatment using the Functional Disability Inventory (FDI) (Walker & Greene, 1991). This questionnaire is frequently used in research and in the clinic to evaluate disabilities associated with pain. Disabilities are known to be an important factor in chronic pain, having important consequences on the social, emotional, and physical well-being of chronic pain patients.

2.4.3 Brain activation and connectivity

Changes in brain function associated with CRPS has been previously highlighted in the literature. In this study, brain activation at rest and during a sensory task, in which participants will evaluate the intensity and unpleasantness of visual, auditory, and tactile stimuli, will be analyzed to define, first, the effect of the severity of CRPS symptoms and, second, the effect of treatment. In addition, functional connectivity at rest and structural connectivity will be measured.

Taken together, these outcome measures will allow us to have an accurate representation of the effect of treatments.

3 Study design

3.1 Overview

This is a basic science investigation of potential psychosocial, sensory, and brain markers predicting trajectory of short-term and long-term recovery in pediatric CRPS following both inpatient and outpatient treatment.

The usual inpatient treatment lasts on average three weeks and includes physical, occupational, and recreational therapy, as well as psychotherapy, while patients keep their regular pharmacological treatment. The usual outpatient treatment lasts on average several months and includes physical therapy and psychotherapy, in addition to pharmacotherapy. For both inpatients and outpatients, the primary anti-neuropathic pharmacotherapy typically includes gabapentin, pregabalin, or amitriptyline, or, less frequently, duloxetine. It is important to note

that this study is not designed to investigate the efficacy of treatment *per se*, instead it aims to predict trajectory during the course of treatment as usual. This study is primarily mechanistic and does not include any intervention or modification of treatments. Therefore, patients, who are scheduled for regular inpatient or outpatient treatment of CRPS, are free to refuse to enroll without any consequences for the scheduled treatment.

The investigated markers will be assessed in patients undergoing inpatient or outpatient treatments. To define potentially relevant markers, measurements in patients will be compared to the same measurements in healthy children. For this purpose, participants will undergo a testing session just before the beginning of their treatment or as close as possible from the beginning of their treatment.

To establish the influence of potential markers on short-term recovery, patients will undergo an additional session upon completion of their treatment. To investigate the effect of the previously defined markers on long-term recovery, patients will complete a third session at six months after treatment. For comparison purposes, healthy control children will undergo sessions following the same schedule as the patients. To assess the association between symptoms of CRPS in children and social environment, at least one parent of each enrolled child will be asked to complete three sessions following the same schedule as their child.

Each testing session will include self-reported questionnaires for the children and their parents and a brain imaging session for the children. Each session will last approximately three hours for the children and 1.5 hour for the parents. Additional sessions might be scheduled in case of equipment failure.

To avoid distraction or psychosocial influences, participants to these studies will be alone with the experimenter during the sessions, with the exception of the consenting/assenting part of the study and the completion of the medical history and MRI screening forms. Similarly, parents will be left alone in a room while completing questionnaires. In addition, participants and their parents will be asked to shut down their cellphones and other electronic devices during the sessions to further avoid distraction.

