Pediatric Complex Regional Pain Syndrome (CRPS) is a severe and complex type of pediatric chronic pain, which impacts majorly the children's and their families' lives (McClain & Suresh, 2011). CRPS is divided into Type I and Type II, which are differentiated by the absence (Type I) or presence of a discreet nerve injury (Type II) (Harden et al., 2010). CRPS is treated, in the first instance, with outpatient multidisciplinary interventions (Carter & Threlkeld, 2012; Dickson, 2017; Katholi, Daghstani, Banez, & Brady, 2014; Maihöfner, Seifert, & Markovic, 2010). However, several psychosocial factors, such as pain catastrophizing, depression, and/or familial environment, can affect pain symptoms and recovery (Bruehl & Chung, 2006; Cruz, O'Reilly, Slomine, & Salorio, 2011; Vervoort, Trost, & Van Ryckeghem, 2013). In such cases, more intensive interventions necessitating hospitalization are necessary to help the patients (Dickson, 2017). Defining which factors predict the trajectory of recovery could allow for better targeting of the treatment that a patient needs to successfully recover. In this study, the effect of psychosocial and sensory factors and possible brain markers predicting changes in pain symptoms before – after treatment will be investigated in children diagnosed with CRPS and currently undergoing the usual inpatient or outpatient treatment at CCHMC. In addition, brain changes before – after treatment will be analyzed, as well as potential psychosocial influences on these changes. To establish a baseline of changes associated with CRPS recovery, potential psychosocial and sensory markers, as well as brain activation and connectivity in CRPS patients will be compared to healthy children. To assess the psychosocial environment, parents of children enrolled in the study will complete a series of questionnaires.

For this purpose, we define the following specific aims to investigate in a main study:

1.1 Specific aim 1

Identify changes in psychosocial, psychophysical, sensory, and cerebral characteristics associated with CRPS.

Psychosocial, psychophysical, sensory, and cerebral measurements in children diagnosed with CRPS will be compared with such measurements in healthy children before or at the beginning of an inpatient or outpatient treatment at CCHMC.

We hypothesize that children diagnosed with CRPS will differ from healthy children in their responses to psychosocial, psychophysical, sensory, and cerebral measurements.

1.2 Specific aim 2

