3.2 Study sessions

The study described in this protocol will include up to three sessions. Each session will include the same testing components. Only the timing of the sessions differs (Figure 1). The timing of the sessions will be scheduled following the normal duration of the inpatient or outpatient treatment. No intervention will be scheduled during the regular inpatient or outpatient treatment at the FIRST clinic or at the Pain Management Center. In addition, no alteration of the usual inpatient or outpatient treatment associated with this study will occur.

Figure 1. Timeline of sessions

3.2.1 *First session*

The first session will take place right before or as early as possible during the inpatient or outpatient treatment of children diagnosed with CRPS.

Demographic information and medical history of the children and their parents will be reviewed with participants and their parents. A urine sample may be collected from female participants to test for pregnancy if they are post-menarchal. A urine sample will also be collected from all participants to assess the usage of non-prescribed drugs/substances. Healthy participants with positive tests for opioids or other analgesics will be excluded. In addition, participants and their parents will complete questionnaires assessing their psychological wellbeing, responses to pain, and influence of their social environment. Current pain sensations will be assessed in patients with CRPS by recording ratings of pain intensity and unpleasantness on VAS. To assess the extent of their pain, participants will report affected body parts on a picture of themselves and fill in the Pain and Symptom Assessment Questionnaire.

Participants will then undergo a brain MRI scan, during which fMRI, DTI, pCASL, and/or anatomical images will be collected to assess brain changes underlying CRPS. While in the

scanner, scans will be performed during rest and during tasks, including quantitative sensory testing and a multisensory visuo-audio-motor task.

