4.3 Participant withdrawal criteria

For all child participants

1. Participants are unable to adequately communicate and understand the consent form and instructions given to them.

2. Participants decline further participation in the study.
3. Participants are unable to keep the appointments.
4. Participants fail to comply with experimental protocol or instructions.
5. Identification of brain, neurologic, or severe psychiatric abnormalities beyond those normally associated with chronic pain.
6. Experimenter assesses that withdrawal from the study is in the participant's best interest.
7. Patients fail to adequately comply with or complete sufficient portions of their treatment.
8. Healthy control participants are using opioid or other analgesic drugs (positive drug test).

For parent participants

1. Participants are unable to adequately communicate and understand the consent form and instructions given to them.
2. Participants decline further participation in the study.
3. Participants are unable to keep the appointments.
4. Participants fails to comply with experimental protocol or instructions.
5. Their child declines further participation in the study.
6. Experimenter assesses that withdrawal from the study is in the participant's best interest

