5.1.2 Analyses of behavioral and psychophysical data

Questionnaires data will be scored and used to characterize patients-control differences and serve as potential covariates in current and future analyses.

The effect of behavioral factors on the trajectory of our outcome measures, i.e. changes in pain ratings, in functional disabilities over time, and brain function and structure, might be assessed by multilevel regressions and mixed ANOVAs. Post-hoc analyses will be performed when appropriate.

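### Aim 1 ascribes baseline patient-control differences to CRPS, but the planned contrast cannot separate disease effects from the effects of patients' continuing medication

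*Combined protocol and SAP*

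**What the plan says.** Section 1.1 sets Aim 1: "Identify changes in psychosocial, psychophysical, sensory, and cerebral characteristics associated with CRPS". Children with CRPS are compared with healthy children before or at the start of treatment. Section 3.2.1 is firmer about the session-1 scans: "images will be collected to assess brain changes underlying CRPS".

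On medication the two sides of the comparison have different rules.

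- **Controls.** Section 3.2.1: "Healthy participants with positive tests for opioids or other analgesics will be excluded". Item 8 of section 4.3 repeats this as a withdrawal criterion and applies it to healthy controls only.
- **Patients.** Section 3.1 says that inpatient therapy proceeds "while patients keep their regular pharmacological treatment" and lists pharmacotherapy as part of outpatient care. For both groups, "the primary anti-neuropathic pharmacotherapy typically includes gabapentin, pregabalin, or amitriptyline, or, less frequently, duloxetine". The study "does not include any intervention or modification of treatments".

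Section 4 matches the groups on BMI, sex and age. Section 5.1.2 states: "Questionnaires data will be scored and used to characterize patients-control differences"; those scores are also the only covariates it names. Section 5.1.1 names no covariate for the imaging models. Medical history is reviewed at session 1, but no analysis uses medication from it.

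Section 7.1.4, in its paragraph on burn risk, says that no participant will have analgesic medication. This conflicts with section 3.1 as regards the patients.

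**The concern.** The listed drugs act on the central nervous system and are given to alter pain processing. Resting BOLD, cerebral blood flow, thermal thresholds and suprathreshold ratings are the kind of measure on which they could act. If patients are medicated and controls are not, a session-1 difference may reflect the disease, the drugs or both. A drug effect opposite in sign to the disease effect could hide a real difference.

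The problem exists at session 1 even if no prescription changes during follow-up. What is at stake is the Aim 1 conclusion: a difference of treated patients from healthy children would be reported as a feature of CRPS.

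**Working it through.** **1. Is the asymmetry in the text?** Yes. Analgesic exclusion applies to controls (3.2.1; 4.3 item 8). Patients have no corresponding rule and their treatment is not modified (3.1).

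**2. Does anything separate drug from disease?** No. Medication is not a matching factor (4), a covariate, a stratum or a subgroup (5.1.1, 5.1.2).

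**3. How large could the effect be?** The plan has no figure on this point to reproduce. Its group sizes are the only document inputs:

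- 21 per group enrolled (5.2), so 42 patients v 21 controls if the two patient groups are pooled. Pooling is my assumption.
- 18 per group before the 15% allowance (18 × 1.15 = 20.7, rounded to 21), so 36 v 18.
- Share medicated *p* and drug effect *d* in SD units are assumed.

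With no true CRPS effect, the patient mean shifts by *p* × *d*. The noncentrality of the two-sample t-test is *p* × *d* × √(n₁n₂/(n₁+n₂)). For 42 v 21, √(42 × 21/63) = √14 = 3.742, with 61 degrees of freedom. The small extra spread from mixing medicated and unmedicated patients is ignored.

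| Share medicated | Drug effect | Mean shift | Noncentrality | False-difference rate, 42 v 21 | 36 v 18 |
|---|---|---|---|---|---|
| 50% | 0.2 SD | 0.10 | 0.37 | 6.6% | 6.3% |
| 70% | 0.5 SD | 0.35 | 1.31 | 25.2% | 22.2% |
| 90% | 0.8 SD | 0.72 | 2.69 | 75.5% | 68.7% |

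Those rows raise both inputs together. Varying them separately, for 42 v 21:

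| Drug effect | 50% medicated | 75% | 100% |
|---|---|---|---|
| 0 | 5.0% | 5.0% | 5.0% |
| 0.2 SD | 6.6% | 8.6% | 11.4% |
| 0.5 SD | 15.1% | 28.2% | 45.3% |
| 0.8 SD | 31.3% | 59.9% | 83.8% |

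**4. What would a medication term cost?** With the term set to zero for all controls, the group coefficient compares unmedicated patients with controls. Its standard error, relative to the unadjusted contrast, is √(1/n_unmed + 1/21) / √(1/42 + 1/21). The denominator is 0.267.

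- 50% medicated: n_unmed = 21, 0.309/0.267 = 1.15
- 70% medicated: n_unmed = 12.6, 0.356/0.267 = 1.33
- 90% medicated: n_unmed = 4.2, 0.535/0.267 = 2.0
- 100% medicated: the design matrix has rank 2 of 3, so the two effects cannot be separated.

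**The case against.** The strongest reply is that the documents show no actual bias. They give no medicated share, no drug effect and no direction. Section 3.1 lists which drugs are typical, not how many children take them at session 1. This stands, and it limits the point in several ways.

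- A reader might infer that drug effects will be counted as disease effects. The documents support only that the two cannot be told apart.
- A reader might infer that drug exposure coincides almost completely with group. Continuing regular drugs is explicit for inpatients only. Outpatient pharmacotherapy is part of the treatment, and session 1 may come just before treatment starts, so some outpatients may be unmedicated.
- A reader might infer that controls are verified free of these drugs. The urine test is described as covering non-prescribed substances, and the documents do not say whether it detects the four named drugs. The exclusion for analgesics is nevertheless stated.
- A reader might infer that the Aim 2 predictors inherit the bias. Section 3.1 uses controls to help define candidate markers, but Aim 2 relates baseline variables to change in patients' symptoms. A spurious patient-control difference does not by itself make a predictor, and carry-over is not shown.
- A reader might take the percentages as imaging error rates. Section 5.3 plans cluster-based whole-brain inference, to which a single t-test does not transfer.

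Two further replies do not remove the concern. Section 7.1.4 says that participants will have no analgesics, but it is a burn-risk statement, it contradicts section 3.1, and no procedure in the documents brings it about. The other reply is that the study deliberately observes usual care. That supports describing the results as those of treated CRPS. It does not support an unqualified attribution to the disease.

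**Conclusion.** The concern holds as a limit on attribution. As planned, the Aim 1 contrast compares CRPS under usual pharmacotherapy with healthy children excluded for analgesics, and nothing in the design or analysis separates drug from disease.

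The size is unknown. Under the assumed inputs, the false-difference rate for one pooled t-test runs from about 7% through 25% to 76%, against a nominal 5%; it stays at 5% if the drugs have no effect on the measure. These figures rest on assumed shares and effects, on pooling the two patient groups, and on there being no true CRPS effect. The documents do not establish that any Aim 1 difference would be due to drugs.

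The study's primary aim, prediction of recovery in patients, is not shown to be affected. The change should be made because the planned wording claims more than the comparison can support and the remedy is cheap.

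**What to change.** 1. Code current centrally acting medication (yes/no by drug class) from the session-1 medical history, and state in section 3.2.1 that the history captures it.
2. In sections 5.1.1 and 5.1.2, keep the planned patient-control contrast as primary. For each Aim 1 measure add a sensitivity model with a medication term (zero for controls), and report the on-drug v off-drug difference within patients.
3. Describe Aim 1 differences as those of CRPS under usual pharmacotherapy. Report the sensitivity results beside them, without making them a pass/fail condition. A rule that sign and size must hold would need a tolerance, is undefined for whole-brain maps, and could rest on about 4 unmedicated patients at 90% medicated.
4. Reconcile section 7.1.4 with section 3.1 on patients' analgesic medication.

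The cost is some SAP wording and a few yes/no codes from a history already taken. The sensitivity estimate is less precise (standard error about 1.15, 1.33 and 2.0 times as large at 50%, 70% and 90% medicated) and cannot be obtained if every patient is medicated. It also remains open to confounding by indication, since unmedicated children may differ in severity. No change to any child's treatment is implied.

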3.2 Study sessions

The study described in this protocol will include up to three sessions. Each session will include the same testing components. Only the timing of the sessions differs (Figure 1). The timing of the sessions will be scheduled following the normal duration of the inpatient or outpatient treatment. No intervention will be scheduled during the regular inpatient or outpatient treatment at the FIRST clinic or at the Pain Management Center. In addition, no alteration of the usual inpatient or outpatient treatment associated with this study will occur.

Figure 1. Timeline of sessions

3.2.1 *First session*

The first session will take place right before or as early as possible during the inpatient or outpatient treatment of children diagnosed with CRPS.

Demographic information and medical history of the children and their parents will be reviewed with participants and their parents. A urine sample may be collected from female participants to test for pregnancy if they are post-menarchal. A urine sample will also be collected from all participants to assess the usage of non-prescribed drugs/substances. Healthy participants with positive tests for opioids or other analgesics will be excluded. In addition, participants and their parents will complete questionnaires assessing their psychological wellbeing, responses to pain, and influence of their social environment. Current pain sensations will be assessed in patients with CRPS by recording ratings of pain intensity and unpleasantness on VAS. To assess the extent of their pain, participants will report affected body parts on a picture of themselves and fill in the Pain and Symptom Assessment Questionnaire.

Participants will then undergo a brain MRI scan, during which fMRI, DTI, pCASL, and/or anatomical images will be collected to assess brain changes underlying CRPS. While in the

scanner, scans will be performed during rest and during tasks, including quantitative sensory testing and a multisensory visuo-audio-motor task.

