Develop predictors of short-term and long-term recovery from CRPS using psychosocial measures, sensory sensitivity, and brain function and structure.

Changes in symptoms of CRPS, such as pain and functional disabilities, will be investigated in relation to potential psychosocial, sensory, and brain markers. Variables obtained at baseline will be examined for significant relationship with recovery.

1.3 Specific aim 3

Investigate the evolution of changes in psychosocial, psychophysical, sensory, and cerebral measures, associated with CRPS.

Short-term and long-term changes in psychosocial, psychophysical, sensory and cerebral measures in children diagnosed with CRPS will be compared to changes in healthy children.

We hypothesize that differences in psychosocial, psychophysical, sensory and cerebral measures between children with CRPS and healthy children will be reduced immediately after treatment, as well as six-month post treatment.

2 Background information

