4.1 Inclusion criteria

For all child participants

1. 10-17 years old
2. fluent in English

For inpatient participants

1. Diagnosis of CRPS
2. Previous unsuccessful attempt(s) of treatment
3. Scheduled for or beginning an intensive therapy at the FIRST clinic following the clinic's regular treatment plan

For outpatient participants

1. Diagnosis of CRPS
2. Scheduled for or beginning an outpatient treatment for CRPS at the Pain Management Center following the center's regular treatment plan

For healthy controls

1. No chronic pain diagnosis

For parents

1. Fluent in English
2. Child enrolled in the study

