4.5 Recruitment / Enrollment Procedures

Participants will be recruited via word-of-mouth, internet, email, printed and/or broadcast CCHMC-approved advertisements in the community as well as contact from the volunteer database of the Clinical Trials Office. Recruitment will be continuous through the course of the study. If necessary to obtain adequate minority representation, under-represented racial groups might be targeted specifically for recruitment. Potential participants will undergo telephone screening to ensure that they meet the inclusion/exclusion criteria. If potential participants choose not to enroll or fail to meet inclusion criteria, all PHI will be destroyed.

Potential participants from the outpatient and inpatient clinics will be approached during the planning of their treatment at CCHMC by their clinical provider. If the patients express interest for the study, experimenters will contact them to confirm interest and assess eligibility.

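### Session 1 may fall after treatment has begun, yet it is the baseline for recovery and the source of the Aim 2 predictors, and no planned analysis accounts for the delay

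*Combined protocol and SAP*

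**What the plan says.** Four places in the protocol allow the first assessment to follow the start of treatment.

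- Section 3.2.1: "The first session will take place right before or as early as possible during the inpatient or outpatient treatment of children diagnosed with CRPS".
- Section 3.1: "participants will undergo a testing session just before the beginning of their treatment or as close as possible from the beginning of their treatment".
- Section 1.1, for the comparison with healthy children: "before or at the beginning of an inpatient or outpatient treatment at CCHMC".
- Section 4.1, outpatient eligibility: "Scheduled for or beginning an outpatient treatment for CRPS at the Pain Management Center". The inpatient criterion is worded in the same way.

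Session 2 comes at the end of treatment and session 3 six months later (Section 3.2.2). Under Aim 2 (Section 1.2), "Variables obtained at baseline will be examined for significant relationship with recovery". Section 5.1.2 defines the outcomes as change in pain ratings, disability and brain measures, to be examined possibly by multilevel regression or mixed ANOVA. The only covariates it names are questionnaire scores. Sections 5.1 to 5.4 contain no term for time since treatment start and no analysis limited to children assessed before treatment. The measurement schedule in Section 3.2.4 lists no treatment-start date.

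On course length, Section 3.1 says "The usual inpatient treatment lasts on average three weeks" and "The usual outpatient treatment lasts on average several months".

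**The concern.** Session 1 does two jobs. It is the reference point for every change score, and it supplies the markers meant to predict that change. If a child has already had some treatment, the change score omits whatever happened before the visit, and the marker may reflect early response as well as the state before treatment.

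Aim 2 is the most exposed, because a predictor should precede the response it predicts. Aim 1 is affected because the contrast with healthy children may be taken in partly treated patients. Aim 3 is affected because patients' change is set against change in healthy children, who have no treatment start. The protocol's own background (Section 2.1) says intensive programmes are associated with less pain and disability and with central changes, so early movement in these measures is plausible.

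The same number of days is also a much larger fraction of a three-week stay than of a course lasting months.

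**Working it through.** **The plan's own figures.** The plan gives no figure for the delay. Its behavioral sample size reproduces as a repeated-measures group-by-session interaction with 3 groups, 3 sessions, f = 0.25 and alpha = 0.05, assuming a correlation of 0.5 between sessions and sphericity (neither is stated). λ = f²·N·m/(1 − ρ) = 0.0625 × 54 × 3 / 0.5 = 20.25 on 4 and 102 degrees of freedom. Power is 95.8% at N = 54 and 94.6% at N = 51. Adding 15% gives 18 × 1.15 = 20.7, so 21 per group and 63 in all. Nothing below alters these numbers.

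**Inputs for the delay.** Inpatient course T = 21 days (Section 3.1). Outpatient course T = 90 to 180 days, an assumption because the protocol gives no number. Delay d = 2, 5 or 7 days, chosen only to show a range.

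**Share of within-treatment change missed.** If change is linear, the share is d/T. If it is front-loaded (illustrative, assumed), the share is (1 − e^(−3d/T)) / (1 − e^(−3)).

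| Delay | Course shape | Inpatient, 21 days | Outpatient, 90 days | Outpatient, 180 days |
|---|---|---|---|---|
| 2 days | linear | 9.5% | 2.2% | 1.1% |
| 5 days | linear | 23.8% | 5.6% | 2.8% |
| 7 days | linear | 33.3% | 7.8% | 3.9% |
| 2 days | front-loaded | 26.2% | 6.8% | 3.5% |
| 5 days | front-loaded | 53.7% | 16.2% | 8.4% |
| 7 days | front-loaded | 66.5% | 21.9% | 11.6% |

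A one-day inpatient delay under linear change misses 1/21 = 4.8%, which is minor.

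**When the imbalance disappears.** The two groups miss equal shares when the outpatient delay is T/21 times the inpatient delay: 90/21 = 4.3 times or 180/21 = 8.6 times (60/21 = 2.9 times if the outpatient course is only 60 days). Three inpatient days then match about 13 or 26 outpatient days (about 9 for the 60-day course). Beyond that point outpatients miss the larger share.

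**Leakage into predictors.** Let E be the change before session 1, L the change after it, and X = X₀ + cE the observed marker, where X₀ has no prognostic value. The covariance of X with the outcome L is c·cov(E, L), so for positive c its sign is that of cov(E, L). If early and later change are fixed shares p and 1 − p of one response R, with X₀ and R of equal variance, the spurious correlation is cp/√(1 + c²p²). For c between 0.5 and 1 on a 21-day course:

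- 1 day: 0.02 to 0.05
- 3 days: 0.07 to 0.14
- 7 days: 0.16 to 0.32

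If early responders have less left to gain, cov(E, L) is negative and the artefact runs the other way.

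**The case against.** The strongest reply is that the protocol already restrains the delay. Session 1 is to be held as near the start as can be managed, and patients "will be approached during the planning of their treatment at CCHMC by their clinical provider" (Section 4.5). Long inpatient delays fit poorly with that intention, and it would be wrong to say there is no limit at all. This stands. What is missing is a maximum number of days in the text. Figure 1, the session timeline, could not be read for this point, so a window there cannot be excluded.

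A reader might infer that recovery is understated, mainly in inpatients. The documents do not support that. Understatement requires improvement in the first days, and an early flare would reverse the sign. The inpatient emphasis requires similar delays in days, and none are given.

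A reader might also infer that predictive value is inflated. The outcome excludes the early response, so the association could strengthen, weaken or reverse. The leakage figures rest on an assumed coupling. With 42 patients, a correlation of about 0.30 is needed for significance at 5%, which only the most extreme case above exceeds.

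It is also fair that no aim compares inpatients with outpatients, and that under linear change a delay common to a whole group rescales every change score and leaves correlations within that group intact, measurement noise and leakage into the marker aside. Variation in delay between children, and pooling of the two patient groups, remain exposed.

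Finally, multilevel regression can use actual assessment times. Nothing in Section 5.1.2 forbids this, but nothing plans it.

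**Conclusion.** The point holds as a possible bias of unsettled direction. The protocol permits session 1 after treatment starts, relies on it both as baseline and as the source of predictors, and plans no analysis that accounts for the delay. Following the rule as written can therefore mix early response into baseline values.

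At equal delays in days, the share of the course missed is larger for inpatients: 10%, 24% or 33% at 2, 5 or 7 days, against about 1% to 8% for outpatients. This rests on linear change, a 21-day inpatient course and an assumed 3 to 6-month outpatient course. The effect is small at one day and grows if response is front-loaded. Because the actual delays and the shape of early response are unknown, neither the size nor the sign of the bias can be fixed from the documents, and that is the main reason to record the delay. This is a cheap improvement that should be made. It does not touch the sample size.

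**What to change.** Keep the flexible window and make these changes:

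1. Record the number of treatment days received before session 1, and report its distribution by treatment group.
2. In Aim 2 models, fitted in patients only, include the delay and its interaction with treatment group.
3. In longitudinal models, let the delay modify change through a delay-by-session term among patients. Do not enter it as a plain main effect across patients and healthy controls. Controls have no treatment days, so the term would be undefined or tied to group, and a main effect adjusts level rather than change.
4. Repeat the main Aim 2 and Aim 3 analyses in patients assessed before their first treatment day, keeping the healthy controls for Aim 3.

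The cost is one date field, a few extra model terms and a sensitivity analysis. With at most 2 × 21 = 42 patients, that analysis will be smaller and less precise, and the extra terms will be imprecisely estimated. Recruitment, visits and treatment are unchanged.
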